The significance of this study is to evaluate the efficacy of OnabotulinumtoxinA (BOTOX®) for the treatment and prophylaxis of pediatric migraine in a randomized, double-blinded, placebo cross over study. No trials currently exist in literature studying OnabotulinumtoxinA for efficacy and/or safety for indication of pediatric migraine, although significant contributions have been made by retrospective case series over the last 10 years. The historical and longitudinal context of the interest to design this study comes from the Principal Investigator's (PI) extensive use of "off label" OnabotulinumtoxinA to treat refractory pediatric migraine over the last 5 years. Anecdotally, the results are so impressive and impactful in her patients' lives, that this therapeutic ought to be studied in a controlled setting to demonstrate clinical outcome to validate existing treatment strategies. Thus, this study seeks to fulfill ASRA's goal of identification of novel applications of existing therapeutics. Moreover, this trial may benefit an under-studied pain population with the long-term goal of new FDA indication to "on label" status. The proposal also carries policy and legislative impact as it fulfills the federal initiative to design and conduct trials in the pediatric pain population within confines of the Best Pharmaceuticals for Children Act (BPCA) of 2002. The goal of the BPCA Program is to improve pediatric therapeutics through preclinical and clinical drug trials that lead to drug labeling changes.

3. Describe the purpose, specific aims or objectives. Specify the hypotheses or research questions to be studied.

Specific Aims

The proposed research is intended to explore whether pediatric chronic migraine may benefit from OnabotulinumtoxinA treatment. The study is focused on a specific debilitating disorder of chronic pain in a well-defined population that is historically not well studied. The objectives are attainable within the proposed timeframe.

Hypothesis:

Aim 1: To test if OnabotulinumtoxinA is superior to placebo in reducing headache frequency, intensity and pediatric migraine-related disability (Efficacy)

Aim 2: To evaluate the incidence of adverse events of OnabotulinumtoxinA administration in children aged 8-17 (Safety, Tolerability)

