Aim 3: To evaluate if OnabotulinumtoxinA can contribute to reduction in preventive and rescue medication, reduction in health care utilization via emergency room and hospital admissions and health care costs (Hospital and pharmacy resource utilization)

Study aims fit together in an overall framework such that primary and secondary outcomes are easily defined, measureable, and validated as an acceptable means to measure clinical success and to longitudinally assess response.

4. Describe the primary outcome variable(s), secondary outcome variables, and predictors and/or comparison groups as appropriate for the stated study objectives/specific aims.

Primary outcome: Absolute number of headache days per month.

Secondary outcomes

- Severity of headache episode
- Disability scoring (PedMIDAS)
- Duration of benefit assessed at every 6 week interval
- Change from baseline in the frequency of severe headache days
- Change from baseline in the total cumulative hours of headache on headache days Change from baseline in the total dose or interval of preventive migraine or rescue migraine medication
- Percentage of patients with $\geq 50\%$ decrease from baseline in the frequency of headache days
- Percentage of patients who are prescribed oral rescue migraine prophylactic treatment
- Percentage of patients who reduce consumption of preventive migraine or rescue migraine treatment
- Change from baseline in the absolute ED visits and/or hospital admission during each treatment phase
- Percentage of patients experiencing associated adverse events, serious or non-serious. (Non-serious defined as injection site swelling, redness, temporary pain, ptosis, blurred vision, worsening of migraine, nausea, vomiting, head lag weakness, drooling.)

5. List up to ten relevant references/articles to support the rationale for the research. Do not append an extensive NIH-grant-style bibliography.

1. Aurora, S.K., et al., *OnabotulinumtoxinA for treatment of chronic migraine: pooled analyses of the 56-week PREEMPT clinical program*. Headache, 2011. **51**(9): p. 1358-73.
2. Dodick, D.W., et al., *OnabotulinumtoxinA for treatment of chronic migraine: pooled results from the double-blind, randomized, placebo-controlled phases of the PREEMPT clinical program*. Headache, 2010. **50**(6): p. 921-36.
3. Ahmed, K., et al., *Experience with botulinum toxin type A in medically intractable pediatric chronic daily headache*. Pediatr Neurol, 2010. **43**(5): p. 316-9.

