investigator's discretion, an additional 40U may be administered using a follow-the-pain strategy. The maximum dose will be **155 U across 31 sites**. All treatments will be performed by the PI.

2. Provide precise definitions of the study endpoints and criteria for evaluation; if the primary outcomes are derived from several measurements (i.e., composite variables) or if endpoints are based composite variables, then describe precisely how the composite variables are derived.

Primary outcome variables:

- Pain scores: as a standard part of the procedure, patients are asked to record their pain scores before and after their procedure. The principal endpoints are intensity on a 10 point NRS scale (VAS where needed), and frequency of migraine episodes in a 30 day period. This will be compared to baseline data pre-injection. For the study, pain score data will be collected up until the last follow up of the last injection of each patients' Botox ® injection series.
- Duration of benefit from the Botox ® injections: reduction in pain score by greater than or equal to 30%
- Functionality: the extent of normal activity able to be performed by a patient
- Disability: inability to function normally, physically or mentally
- Opioid consumption: amount of opioid medication consumed
- Neuropathic/migraine medication consumed including immediate release NSAID

Secondary outcome variables:

- Quality of pain: continuous, intermittent, throbbing, etc.
- Associated side effects: nausea, vomiting, food intake, diarrhea, constipation, anxiety, depression and/or adverse events associated with study drug
- Psychological history i.e. anxiety, depression
- Neuropathy: any weakness, numbness, and pain from nerve damage, usually in the hands and feet
- Type of analgesia/anesthesia: analgesic/anesthetic medication(s) used during procedure

Incidence of hospital admissions

- Incidence of ER visits
- Current medication use

Other variables:

- Neurological workup: Neurological medical evaluation, including medical history, physical examination, medical tests, survey of the patient's medical record for any information regarding Neurological disease
- Diagnosis: identification of chronic migraine head pain
- Indications: reason for Botox ® injections, number of injections in the Botox ® injection series
- Procedure: specific procedure including location of procedure, imaging information, and other specific procedure information

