After enrollment, each subject will begin with a 28 day baseline screening phase followed by a 24 week double-blind, placebo-controlled, randomized AB|BA crossover period, followed by a second 24-week open-label period where all subjects will receive treatment with OnabotulinumtoxinA. There will be one treatment at the beginning of each 12 week block, meaning 4 treatments over the 48 week study period total. Those assigned to the AB group will receive OnabotulinumtoxinA in the first treatment and saline placebo in the second, those in the BA group will receive saline and then OnabotulinumtoxinA. Both groups will then receive OnabotulinumtoxinA in the last two treatments. Progress check-ups will occur every 6 weeks during the study; participants will be asked to complete the Pediatric Migraine Disability Assessment (PedMIDAS) survey.

3. List data collection instruments (e.g., measures, questionnaires, interview questions, observational tool, etc.).

Investigator-authored, non-standardized, or un-validated measures must be submitted for review.

Data will be collected using a diary provided to the subject enrolled in the study. The participants will be asked to record the frequency and intensity of any neurological pain that occurs for the duration of the study. Progress check-ups will occur every 6 weeks during the study; participants will be asked to complete the Pediatric Migraine Disability Assessment (PedMIDAS) survey.

D. UCIMC Supplementary Clinical Services

If a UCIMC clinical unit/department (e.g., phlebotomy for blood draws, pharmacy for dispensing study drug(s), radiation services for X-rays, MRIs, CT scans, and Neurology for lumbar punctures) will perform research-related procedures:

1. List the research procedure (e.g. lumbar puncture, MRI, CT Scan), and
2. Identify the unit/department that will perform the procedure.

Not applicable: This study does not involve the services of a UCIMC clinical unit/department.

E. Privacy

Privacy is about the subject's ability to control how much others see, touch, or collect information about the subject. Indicate all of the following methods that will be used to assure subject privacy. *Violations of privacy include accessing a subject's private information without consent, asking personal sensitive information in a public setting, being audio recorded or photographed without consent.*

Research procedures (including recruitment) are conducted in a private room.

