1. Describe and assess any reasonably foreseeable risks and discomforts — physical, psychological, social, legal or other. Include an assessment of their expected frequency (e.g., common – 65%, less common – 40%, unlikely – 5%, rare - <1%) and the seriousness (mild, moderate, severe). A *bullet point list is recommended. If this study will involve the collection of identifiable private information, even temporarily, for which the disclosure of the data outside of the research could reasonably place the subjects at risk, include the risk of a potential breach of confidentiality.*

As listed in the Risks section of the Informed Consent.

2. Discuss what steps have been taken and/or will be taken to prevent and minimize any risks/ potential discomforts to subjects. *Examples include: designing the study to make use of procedures involving less risk when appropriate; minimizing study procedures by taking advantage of clinical procedures conducted on the subjects; mitigating risks by planning special monitoring or conducting supportive inventions for the study; implement security provisions to protect confidential information.*

All extracted data will be de-identified immediately and save on a secured database for research purposes only. Study team members will follow strictly the reporting guideline by IRB in case of a breach of confidentiality, which is nearly impossible since all data are de-identified. Regardless, all collected information will be securely stored on a password-protected server.

Subjects for this study will be closely monitored for any potential adverse events. Subjects will be able to call the Lead Researcher 24 hours a day for any potential issues.

C. Potential Benefits

1. Describe the potential benefits subjects may expect to receive from participation in this study. *Compensation is not a benefit; do not include it in this section.*

There is no direct benefit anticipated for the subjects.

There is a prospect of direct benefit to children participating in the study. Taking part in this study may or may not make your health better with the first two treatments. While researchers hope Botox® will be more effective than the standard (usual) treatment, there is limited proof of this yet.

2. Specify the expected potential societal/scientific benefit(s) of this study.

Overriding Rationale

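### Non-serious adverse events are defined by a list of event names with no consequence criterion, so the serious/non-serious split could understate serious events

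*Combined protocol and SAP*

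**What the plan says.** Section 1, item 3 makes safety the second of three aims: "To evaluate the incidence of adverse events of OnabotulinumtoxinA administration in children aged 8-17 (Safety, Tolerability"). Section 1, item 4 turns this into a secondary outcome: "Percentage of patients experiencing associated adverse events, serious or non-serious". A parenthesis follows directly: "Non-serious defined as injection site swelling, redness, temporary pain, ptosis, blurred vision, worsening of migraine, nausea, vomiting, head lag weakness, drooling".

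Hospital use is handled elsewhere in the same list, as "Change from baseline in the absolute ED visits and/or hospital admission during each treatment phase". It serves Aim 3, which concerns "reduction in health care utilization via emergency room and hospital admissions and health care costs".

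Three other places might have supplied a definition of a serious event:

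- Section 6.B.2 gives a second list by name: "Associated side effects: nausea, vomiting, food intake, diarrhea, constipation, anxiety, depression and/or adverse events associated with study drug". It has no seriousness criterion. Hospital admissions and ER visits are separate items there too.
- Section 7.B.1 describes the risks only by reference: "As listed in the Risks section of the Informed Consent". Section 7.B.2 promises close monitoring for adverse events but gives no grading or seriousness rule. Its sentence on IRB reporting concerns breaches of confidentiality.
- Section 6.I.3, on methods for secondary outcomes, is answered N/A.

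**The concern.** Whether an adverse event is serious is a matter of what it led to. Here it is settled by what the event is called. The plan uses the language of definition and does not offer the list as examples. Only two of the ten items carry a qualifier: pain must be temporary, and swelling must be at the injection site. The others, including worsening of migraine, vomiting and head lag weakness, are non-serious without condition.

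Admissions are collected, but nothing connects an admission to the event behind it. The same episode could therefore appear as an admission in the utilisation table and as a non-serious event in the safety table.

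The stake is how the safety result reads. Section 1, item 1 says that no randomised, placebo-controlled safety data exist in children, and Section 7.C.2 gives demonstrating safety as part of the overriding rationale. In a trial of this size, a report of no serious events and a report of one are read quite differently.

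**Working it through.** The plan states no figure on this point, so there is none to reproduce. The check is a reading of the text, followed by a calculation of scale.

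**Reading the rule through**

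1. Suppose a child has worsening of migraine after an injection, it is judged associated with treatment, and the child is admitted.
2. The adverse-event outcome in Section 1, item 4 names worsening of migraine as non-serious. No exception for admission is given there.
3. Sections 6.B.2, 6.I.3, 7.B.1 and 7.B.2 contain nothing that overrides step 2.
4. The child therefore counts in the non-serious percentage and not in the serious percentage.
5. The child still counts once in the total with any adverse event, and the admission still counts, by treatment phase, in the hospital-use outcome.

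Only the serious/non-serious split is exposed.

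**Scale**

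Input: 26 children, from Section 6.C.1 (Patient Population). The documents give no rate at which a listed event leads to admission.

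- One child: 1/26 = 0.038, or 3.8 percentage points.
- With 0 of 26 reported, the exact (Clopper-Pearson) upper 95% limit is 1 − 0.025^(1/26) = 0.132. The interval is 0 to 13.2%.
- With 1 of 26 reported, the exact lower limit is 1 − 0.975^(1/26) = 0.001. The upper limit solves (1 − p)^26 + 26p(1 − p)^25 = 0.025, which gives p = 0.196. The interval is 0.1 to 19.6%.

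If one such child were the only serious case, the literal rule would move the report from the second line to the first.

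The chance that at least one such child occurs depends on a rate that has to be assumed. With children independent, it is 1 − (1 − p)^26:

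| Assumed risk per child of an associated listed event leading to admission | Chance of at least one such child in 26 |
|---|---|
| 1% | 23% |
| 2% | 41% |
| 5% | 74% |
| 10% | 94% |

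These rates are illustrations and do not come from the documents.

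The denominator is also an assumption. Section 3.A allows up to 35 children to be consented, including withdrawals and screen failures, and gives 26 as the number expected to complete or needed. No safety denominator is stated. At the upper bound of 35, one child is 1/35 = 2.9 points.

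**The case against.** The best defence is that the parenthesis was meant only as a list of expected mild reactions. Section 1, item 1 names redness, temporary swelling, temporary pain, ptosis and blurred vision as common events in the paediatric literature, and the first five items of the list match these. Staff who know the usual meaning of serious might never apply the list to an admitted child. That is plausible as to intent, but it is not what the text says, and the other five items do not come from that passage. If it is the intent, the fix simply states it.

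Second, the consent form and the text between the reference list in Section 1 and Section 3 were not available for this review. A definition of a serious event there cannot be excluded. This stands as a limit. Such a definition would still have to be reconciled with the outcome list.

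Third, a reader might infer that Aim 2 as a whole understates harm. The documents do not support that. Aim 2 is worded as the incidence of adverse events, without a serious/non-serious split, and that incidence does not change. The outcome counts only associated events, and an admission for worsening migraine in a child with chronic migraine is not automatically one. The admission also stays visible under Aim 3.

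Fourth, a reader might infer that the listed events are those most likely to lead to admission. The documents give no admission rate for any of them.

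Fifth, since "Both groups will then receive OnabotulinumtoxinA in the last two treatments", each child has three active blocks and one saline block, and a reader might infer that the percentage makes an unfair comparison of drug with saline. The plan states no pooled 48-week comparison of that kind for adverse events. How the outcome is to be tabulated is a separate missing detail.

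**Conclusion.** The point holds as a defect of definition. As written, an associated event on the list that leads to hospital admission is counted as non-serious, and the serious part of the adverse-event outcome could then be too low.

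This is conditional on three things: a listed event leads to an admission, it is judged associated, and staff apply the parenthesis literally. It does not show that serious events will be understated. The amount cannot be computed from the documents. The 3.8 points per child and the two intervals show scale only, and they rest on a denominator of 26.

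**What to change.** Replace the parenthesis in Section 1, item 4 with wording such as:

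> Seriousness is judged by the consequence of the event (death, life-threatening, hospital admission or prolongation, persistent disability, or other medically important event), not by its name. The following are expected events: [existing list].

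Use the same rule for the adverse events in Section 6.B.2, and reconcile both places with any definition in the consent form.

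The wording change is small, and it leaves visits, treatment and sample size as they are. It does need some data work. The reason for each admission must be recorded so that it can be linked to the event. The instruments listed in Section 6.C.3 are a diary of pain frequency and intensity and the PedMIDAS, and neither is described as capturing this. Section 6.F.3 says that medical records are checked throughout the study, which may be a source, but the case report form should have a field for it. The other consequence criteria also need to be captured for each event. The reported serious-event rate may come out slightly higher.

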1. Provide the scientific or scholarly rationale for the research. Describe the relevant background information and the specific gaps in current knowledge that this study intends to address.

Background

Chronic headache and migraine are one of the most common pain complaints in children and adolescents, both to the primary care provider, as well as to the pain physician specializing in pediatric pain disorders. Prevalence of migraine in younger children is approximately 10%, and up to 28% of adolescents suffer from recurrent headaches, the majority of which have migraineous features. [3,4] Aydin et al reported the most common headache presentation in pediatric neurology practices was migraine type, comprising 57.1% of all headaches presenting for initial consultation.[5] Population studies have demonstrated that over 130,000 school days are missed every two weeks and 3 million bedridden days occur per month as a result of pediatric migraine.[6] Common migraine is a debilitating disorder that requires both a plan to reduce the severity of attacks, as well as a prophylactic plan that reduces the frequency of occurrence. Episodic syndromes associated with migraine include recurrent gastrointestinal disturbance, cyclic vomiting syndrome and abdominal migraine, benign paroxysmal vertigo, and benign paroxysmal torticollis.[7] Powers et al demonstrated the negative impact of having childhood migraine on overall quality of life is similar to pediatric cancer, heart disease and rheumatic disease [8] As the frequency of migraine attacks increase, so does proportionally the child's disability in lost school time and family and social interactions, all of which may lead in turn to economic disability. Compared with episodic migraine sufferers, patients with chronic migraine have a lower socioeconomic status, reduced health-related quality of life, greater psychiatric and medical comorbidities, and increased occupational disability. [9] Stang et al estimated the health care costs are 70% higher for a family with a migraine than a non-migraine affected family, and direct medical costs for children with migraine are reported to be similar to those for adults. [6]. A study published in JAMA 2003 found that health care costs, work-related disability for parents and lost educational opportunity for the child leads to an annual economic impact in the US of approximately \$36 billion due to both direct medical costs and lost productivity into adulthood.[10]

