in the pediatric population. In a retrospective case series by Ahmed et al to assess tolerability and efficacy of OnabotulinumtoxinA in 10 female patients aged 11-17 years, four patient reported subjective but clinically relevant relief in headache intensity, and 2 patients noting both decrease in intensity and frequency. The four responders also reported improvements in quality of life. [16] Chan et al prospectively evaluated 12 adolescent females with migraine and chronic daily headache, 6 of which were long term patients. They reported all long term patients had improvement in headache symptoms, which decreased on average 33-75%, and improvement in quality of life. [17] Kabbouche et al also in another retrospective study found statistically significant improvement in monthly headache frequency in 45 pediatric chronic daily headache patients who participated in 252 OnabotulinumtoxinA injections (average dose 188.5 +/- 32 units) and an improvement in pediatric migraine disability. A 30 point improvement in pediatric disability scoring between first injection and follow-up injection was also observed with decreased calculated disability from severe to moderate on PedMIDAS. [18] In a 10-year follow up of case series of OnabotulinumtoxinA intervention in adolescents with chronic daily headache and cervicalgia, Schroeder et al demonstrated both short term efficacy on headache frequency and severity, and in the long term follow up (10 years post injection therapy), chronic daily headache was not existent in any of the patients. [19] Common adverse events of OnabotulinumtoxinA reported in literature in the pediatric population are redness or temporary swelling at injection site, temporary pain at injection site, ptosis, and blurred vision [17]. In all of these studies, completion of a prospective, randomized double blinded placebo controlled trial is highly recommended to demonstrate objective outcome parameters in efficacy and tolerability. In the PI's nearly 5 year experience of using OnabotulinumtoxinA in pediatric practice she has seen dramatic improvement in patient pain (both in intensity and frequency of migraine), duration of action of migraine, school attendance, social interaction, disability and reaching student's intellectual potential by prophylactically treating headache with Botox.

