Where \bar{Y}_{AB} represents the group mean of the respective cross over group periods. Given the adult baseline of 19.9 ± 3.6 headache days per month, the treatment reducing this to 6.6 days and the placebo to 8.4 days and assuming a concomitant reduction in SD since these numbers were not reported in the source manuscript, we find that the effect size for this difference (8.4 vs 6.6 with SD 1.35 for both groups) is 0.554, a Cohen's d of 1.33. A power analysis using a significance level of 0.05 and a power of 0.9 shows that 13 subjects per group will be needed for this study, or a total of 26 subjects (13 per group) if comparison were to be made by direct groupwise testing.

3. Describe the secondary statistical method(s) that will be used to analyze the secondary outcome(s) or endpoints.	N/A
4. If appropriate describe secondary or post hoc analyses of primary outcome(s) or other exploratory analysis.	N/A
5. Sample Size Determination: Explain how the overall target sample size was determined (e.g., power analysis; precision estimation), providing justification of the effect size for the primary outcome based on preliminary data, current knowledge/literature and/or cost consideration; if appropriate, provide sample size justification for secondary outcomes. Power analysis should (at least) match the primary outcome/endpoint.	

Given the adult baseline of 19.9 ± 3.6 headache days per month, the treatment reducing this to 6.6 days and the placebo to 8.4 days and assuming a concomitant reduction in SD since these numbers were not reported in the manuscript, we find that the effect size for this difference (8.4 vs 6.6 with SD 1.35 for both groups) is 0.554, a Cohen's d of 1.33. A power analysis using a significance level of 0.05 and a power of 0.9 shows that 13 subjects per group will be needed for this study, or a total of 26.

SECTION 7: RISK ASSESSMENT AND POSSIBLE BENEFITS

A. Risk Assessment

1. Indicate the appropriate level of review of this study, based upon your risk assessment.
 This study involves greater than minimal risk to subjects and requires Full Committee review. Skip to Section 7.B.
 This study involves no more than minimal risk and qualifies as Expedited research .
2. If this study involves no more than minimal risk, provide justification for the level of review and for all applicable Expedited Categories you have chosen.

B. Risks and Discomforts

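### The single adverse-event percentage for Aim 2 mixes toxin-type effects with possible migraine symptoms, so a Botox-versus-saline comparison of it could understate toxin effects

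*Combined protocol and SAP*

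**What the plan says.** Aim 2 (Section 1, item 3) is to evaluate how often adverse events follow OnabotulinumtoxinA in children aged 8-17. The only outcome in Section 1, item 4 that serves it is "Percentage of patients experiencing associated adverse events, serious or non-serious". The bracket defining non-serious events starts with injection-site swelling, redness and temporary pain, and continues "ptosis, blurred vision, worsening of migraine, nausea, vomiting, head lag weakness, drooling".

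Three other places bear on how to read that list:

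- **Section 1, item 1, paediatric literature.** The common toxin events reported in children are given as "redness or temporary swelling at injection site, temporary pain at injection site, ptosis, and blurred vision". Worsening migraine, nausea and vomiting are absent.
- **Section 1, item 1, Background.** "Episodic syndromes associated with migraine include recurrent gastrointestinal disturbance, cyclic vomiting syndrome and abdominal migraine".
- **Section 6.B.2, secondary outcome variables.** "Associated side effects: nausea, vomiting, food intake, diarrhea, constipation, anxiety, depression and/or adverse events associated with study drug", with no summary measure.

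Section 6.I, item 3 asks the author to "Describe the secondary statistical method(s) that will be used to analyze the secondary outcome(s) or endpoints"; the answer is that this is not applicable. In Section 1, item 4, emergency visits and admissions are to be assessed within each treatment phase. The adverse-event outcome carries no such qualifier.

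**The concern.** A patient-level percentage counts a child once, whichever listed event occurred. If some listed events are symptoms of migraine, a working treatment makes them rarer, and that fall offsets any rise in ptosis, blurred vision, weakness or drooling. In a Botox-versus-saline comparison the two movements partly cancel. Even without efficacy, a child who already counts through nausea cannot count again through ptosis, so the toxin excess shrinks.

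If the percentage is reported only once for the whole study, the difficulty is different. Every child is scheduled for one saline block and three Botox blocks (Section 6.B.1), so one overall figure cannot be attributed to either. Section 7.C.2 gives demonstrating tolerability and safety, beside efficacy, as the overriding rationale, so this affects a stated aim.

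**Working it through.** **Plan's own figures.** The plan gives no adverse-event rate, power or precision. Its only calculated figure is the sample size. With a difference of 1.8 and SD 1.35, d = 1.8/1.35 = 1.33, and a two-sided two-sample t test at 0.05 has power 0.877 with 12 per group and 0.903 with 13. The stated 13 per group is reproduced, and this point does not affect it.

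**Inputs.**
- From Section 6.C.1 (Data Collection), adult figures: baseline 19.9 headache days a month, reductions of 8.4 (toxin) and 6.6 (placebo). Remaining days are 19.9 - 8.4 = 11.5 and 19.9 - 6.6 = 13.3. The ratio is 11.5/13.3 = 0.865, a 13.5% fall. (Section 6.I, item 5 treats 8.4 and 6.6 as values reached; I use the reading as reductions.)
- Assumed: mP and mA, the risk per block of a migraine-type event on saline and Botox; t, the toxin-type risk on Botox, zero on saline; independence of the two within a child. Applying the adult ratio to children's adverse events is also an assumption.

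**Formula.** Pooled risk is mP on saline and 1 - (1 - mA)(1 - t) on Botox.

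**Step 1: mP = 60%, t = 15%, three versions of mA.**

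| Assumption for mA | mA | Pooled Botox | Difference from 60% |
|---|---|---|---|
| Equal event chance per headache day: 1 - 0.40^0.865 | 54.7% | 1 - 0.453 x 0.85 = 61.5% | +1.5 |
| Risk itself falls 13.5%: 0.60 x 0.865 | 51.9% | 1 - 0.481 x 0.85 = 59.1% | -0.9 |
| Falls to 45% | 45% | 1 - 0.55 x 0.85 = 53.25% | about -7 |

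The toxin-type excess is 15 points in every row.

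**Step 2: lower background, risk falling 13.5%.** With mP = 30%, mA = 25.9%. For t = 25%, pooled Botox is 1 - 0.741 x 0.75 = 44.5%, a difference of +14.5 out of 25 points. For t = 15% it is 37.0%, or +7.0 out of 15.

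**Step 3: toxin-type risk cancelled exactly.** Setting the difference to zero gives t = 1 - (1 - mP)/(1 - mA).

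| Relative fall in m | mP = 30% | mP = 50% | mP = 70% |
|---|---|---|---|
| 13.5% | 5.5% | 11.9% | 24.0% |
| 30% | 11.4% | 23.1% | 41.2% |

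**Step 4: no efficacy at all.** The difference is t(1 - m). A 25-point excess becomes 17.5, 12.5 and 7.5 points at m = 30%, 50% and 70%.

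**Step 5: independence.** In the first row of step 1, if toxin effects fell only on children who also had a migraine-type event, the pooled figure would be 54.7% (-5.3 points). If they fell only on the others, it would be 54.7 + 15 = 69.7% (+9.7 points).

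**Step 6: what 26 pairs could show.** The plan has no such test; this only gives scale. With mP = 50%, a 30% relative fall and t = 25%, the pooled figures are 50% and 1 - 0.65 x 0.75 = 51.25%. In 20,000 simulated trials with an exact two-sided McNemar test at 0.05, a significant excess on Botox appeared in about 2% for the pooled outcome and 66% for toxin-type effects alone.

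**Step 7: grouping local reactions with toxin effects.** Saline is injected too. If local reactions occurred in 50% of both blocks (assumed), a 15% toxin risk would show as 1 - 0.5 x 0.85 = 57.5% against 50%, which is 7.5 points. Local reactions therefore need a group of their own.

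**The case against.** The strongest reply is that the text does less than this reading fears. It defines which events count as non-serious; it does not say that only a pooled figure will be shown, and nothing prevents a table by event. Section 6.B.2 lists side effects and neuropathy as separate variables. The word *associated* may mean attributed to the drug, and worsening of migraine most naturally means deterioration, so ordinary headache days in children who enter with at least 15 in four weeks need not count. These points limit the size of the problem but do not remove it: no attribution rule is given, the definition names the migraine-type events, and no table by event or by block is planned.

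Three stronger readings are tempting, and the documents do not support them.

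- **That Botox would look about 7 points safer.** This needs migraine-type events to fall from 60% to 45%. The adult headache-day ratio gives +1.5 or -0.9 instead, and at lower background rates a clear excess remains.
- **That the plan will reach a falsely reassuring safety conclusion.** No comparison of this percentage between Botox and saline is planned; Aim 2 only evaluates incidence. The offset arises if someone makes the comparison.
- **That worsening migraine, nausea and vomiting are disease symptoms and should leave the tolerability result.** The protocol itself names them as adverse events. Its Background sentence concerns episodic syndromes, not symptoms of attacks in chronic migraine. Its literature list also omits head lag weakness and drooling, so absence from that list settles nothing. Removing these events could hide a genuine drug effect.

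**Conclusion.** The point holds in a conditional form. As defined, the Aim 2 percentage joins three kinds of event, and a Botox-versus-saline comparison of it would set any benefit on migraine-type events against toxin-type harm. At a 60% saline rate and a 15% toxin-type rate, the 15-point excess shrinks to about +1.5 points or turns to about -7, depending on how far migraine-type events fall. At a 30% saline rate with a 13.5% fall, roughly half of the excess survives (14.5 of 25 points; 7.0 of 15).

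All of these sizes rest on assumed event rates, on independence within a child, and, where used, on an adult ratio applied to children. The direction does not: with toxin-type risk held fixed, fewer migraine-type events always lower the pooled figure. The primary outcome and the sample size are untouched. The change is worth making because it serves a stated aim at almost no cost.

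**What to change.** Add to the adverse-event outcome in Section 1, item 4, and mirror in Section 6.I, item 3:

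- Each listed event, and serious events separately, will be reported by treatment block: Botox against saline within the 24-week crossover, with the open-label period shown separately.
- Three groups will be summarised separately: injection-site reactions; toxin-type effects (ptosis, blurred vision, head lag weakness, drooling); and worsening of migraine, nausea and vomiting.
- All three groups stay in the Aim 2 tolerability report. The pooled percentage may be shown, but the safety conclusion will not rest on it alone.
- State what *associated* means: all events, or only those judged related to the drug, and by what rule.

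The cost is a table layout and a sentence or two, provided events are recorded by type and date. That proviso needs checking: the text of Section 6.C.3 names the pain diary and PedMIDAS and does not describe how adverse events are captured.
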